4.6 Consent

Consent will be performed in the Montefiore-Einstein Center for Cancer Care Radiation Oncology clinics. The study PI, co-investigators, and key personnel will all participate in providing the informed consent to possible study participants. Study key personnel, which includes the treating radiation oncologists, will identify eligible patients. These personnel will then explain the study, explain the consent form, ask the patient if they have any questions, and confirm that they are willing to participate in the study.

5.1 Statistical Plan and Power Analysis

All analyses will be performed according to intention to treat, where patients are analyzed as randomized. The study statistician will conduct randomization and the study coordinator will hold the randomization key. Baseline characteristics will be compared between the interventional arm and the control arm using 2-sample t-tests for continuous variables and using Pearson's chi square or Fisher's exact tests for categorical variables. Primary endpoint analysis: The primary study endpoint is development of higher grade radiation dermatitis (RD) (grade 2-5) compared to lower grade RD (grade 0-1) during the course of external beam radiotherapy. While grades 3-5 are normally considered "high-grade radiation dermatitis," we will be considering and analyzing grades 2-5 as "higher grade radiation dermatitis" versus grades 0-1 as "lower grade dermatitis." No patients in our previous study experienced grades 4-5 radiation dermatitis, so this grouping will be performed for ease of statistical analysis. Pearson's chi square or Fisher's exact tests will be used to compare the incidence rates of high-grade (grade 2-5) radiation dermatitis between the interventional arm and the control arm to assess whether the intervention is

associated with a lower incidence rate of high-grade RD. Logistic regression models will be used to assess this association while adjusting for covariates including age, gender, BMI, cancer type, radiation dose, and concurrent chemotherapy.

Secondary endpoint analysis: Secondary endpoint, quality of life (QoL), will be assessed before and after the radiotherapy. Paired t-tests will be used to compare the QoL summary score between baseline and at the end of the trial within each arm. The 2-sample t-test will be used to compare the QoL score change from baseline to the end of radiotherapy between the two arms. Linear regression models will be used to compare the changes in QoL scores between the 2 arms while adjusting for covariates including age, gender, BMI, cancer type, radiation dose, and concurrent chemotherapy. Missing data will be minimized by pre-emptively implementing effective participant follow-up strategies and by ensuring optimal data collection. In the subsequent analyses, we will evaluate the type and mechanisms of missing data, for example whether it is missing at random (MAR). Multiple imputations may be used to impute missing data. Results obtained from data with imputation will be compared to those obtained from complete data to assess the influence of missing data. Reasons and characteristics of loss-to-follow-up will be documented and examined in order to assess the extent to which patient attrition could bias our results.

Power Analysis: Based on previous studies, we expect that ~50% of our recruited patients will have breast cancer and ~50% will have head/neck cancer. To control for this, we plan to randomize patients in a stratified manner, so that 30 patients with each subtype of cancer will be recruited into each arm (interventional and control arm). With 30 patients in the interventional arm and 30 patients in the control arm, assuming a significance level (alpha) of 0.05, the study has 0.80 power to detect a minimum difference of 0.29 in the incidence of Grade 2-5 radiation dermatitis between the arms using 2-sided test. The sample size was calculated based on results from a previous study from our lab, in which the incidence rate of grade 2-3 radiation dermatitis in the control arm was 0.38. Assuming a conservative 25% attrition rate in the study, we plan to recruit a total of 80 patients (40 each arm) in order to ensure a final sample size of 60 (30 each arm).

6. Data Monitoring and Safety

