4.4 Study Procedures

This trial will be a randomized controlled trial assessing the efficacy of universal bacterial decolonization in preventing high-grade RD. Therefore, all participants, regardless of baseline culture results, will be 1:1 randomized to one of two arms: the intervention arm and the control arm. The randomization will be performed in a stratified manner within each of the two cancer types (breast cancer or head and neck cancer).

All patients, regardless of treatment arm, will receive a complete history and physical exam during their screening visit. Patients in the control arm will be treated according to standard of care without any RD prophylaxis. Patients in the intervention arm will receive a decolonization regimen, which is accepted as standard of care and commonly used in other patient populations (ICU and prior to orthopedic surgery). The decolonization regimen will consist of intranasal mupirocin ointment to be applied twice daily to the nares and chlorhexidine wash to be used once daily to the body. This combined regimen will be conducted by the patient for 5 consecutive days prior to the start of RT, and will be repeated for an additional five days every 2 weeks for the duration of RT, according to standard of care decolonization methods.⁹ Should a patient experience an adverse reaction to the topical chlorhexidine gluconate solution or mupirocin ointment, the principal investigator may discontinue their participation from the study and, depending on severity of adverse effect, remove the offending agent and treat any resulting rash or skin discomfort. This will not affect their radiation therapy treatment, and they will continue to receive standard of care radiation therapy.

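### Randomisation is stratified by cancer type, but the primary test is unstratified with an open choice between Pearson and Fisher, and the seven-term logistic model has too few events for ordinary maximum likelihood

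*Combined protocol and SAP*

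**What the plan says.** Section 4.4 states that participants "will be 1:1 randomized to one of two arms" and that "The randomization will be performed in a stratified manner within each of the two cancer types (breast cancer or head and neck cancer"). The power paragraph of section 5.1, after giving the expected half-and-half mix of cancer types, adds: "To control for this, we plan to randomize patients in a stratified manner".

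For the primary endpoint, section 5.1 offers either a Pearson or a Fisher test: "exact tests will be used to compare the incidence rates of high-grade (grade 2-5) radiation dermatitis between the interventional arm and the control arm". It mentions no strata and does not say when each test applies. A supporting analysis follows: logistic regression "adjusting for covariates including age, gender, BMI, cancer type, radiation dose, and concurrent chemotherapy". With treatment arm that makes seven terms, and the word 'including' leaves the list open. No method for sparse data is named.

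The power statement is that, with 30 per arm and a two-sided 0.05 level, "the study has 0.80 power to detect a minimum difference of 0.29 in the incidence of Grade 2-5 radiation dermatitis". The control rate is 0.38, which implies 0.09 on intervention.

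**The concern.** There are three linked weaknesses.

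- **Strata not used.** Stratified randomisation balances cancer type between the arms. A test that ignores the strata still uses a variance that includes the difference between cancer types, so it rejects less often than its nominal level. The trial bears the administrative cost of stratifying without the analytical benefit.
- **Two tests, no rule.** Pearson and Fisher can disagree in a trial of this size. If the choice is not fixed beforehand, the primary p-value depends on a decision that could be made after the data are seen. Only one of the two comes close to the stated power.
- **Sparse adjusted model.** This model is the only planned treatment estimate that accounts for the stratification factor. With so few events per coefficient, ordinary maximum-likelihood odds ratios tend to lie too far from 1, which here overstates the benefit. Some fits will have no finite solution.

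**Working it through.** **Inputs from the protocol.** 30 analysed per arm (60 in total; 80 enrolled with 25% attrition); control rate 0.38; difference 0.29, so 0.09 on intervention; two-sided 0.05; about half of each cancer type, hence 15 per cancer type per arm. One sentence in the power paragraph, read literally, would mean 30 of each cancer type in each arm. The stated totals of 60 and 80 rule that reading out.

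**Assumed.** Dermatitis rates by cancer type are not given. Control-rate gaps of 0, 20 and 40 points around a mean of 0.38 are used, with a common odds ratio that gives a mean of 0.09 on intervention:
- gap 0: control 0.38/0.38, intervention 0.090/0.090
- gap 20: control 0.28/0.48, intervention 0.056/0.124
- gap 40: control 0.18/0.58, intervention 0.028/0.152

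**1. The plan's own figure.** Unpooled normal approximation: Φ(0.29/√(0.38×0.62/30 + 0.09×0.91/30) − 1.96) = 0.805. The arcsine method gives 0.795. The stated 0.80 is reproduced, and 60/0.75 = 80 matches the enrolment target. Summing binomial probabilities over all outcomes gives the exact power of the named tests: Pearson (no continuity correction) 0.787, Fisher 0.690.

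**2. Choice of test.** Fisher did not reject where Pearson failed to, so the tests disagree in 0.787 − 0.690 = 9.7% of trials at the design effect (2.2% with no effect). Under the customary rule (Fisher only when an expected count is below 5), Fisher is used in 6.4% of trials and power is 0.776.

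**3. Why ignoring strata is conservative.** With no effect, Pearson uses p̄(1−p̄) = 0.38×0.62 = 0.2356. At a 40-point gap the actual variance within cancer types is (0.18×0.82 + 0.58×0.42)/2 = 0.1956. The effective critical value is therefore 1.96/√(0.1956/0.2356) = 2.15, a two-sided level of about 0.03.

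Exact results come from all 16⁴ outcomes. With m_k the events in stratum k and a_k those in one arm, CMH uses z = Σ(a_k − m_k/2)/√Σ[15·15·m_k(30−m_k)/(30²·29)].

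| Gap (points) | Type I error, Pearson | Type I error, CMH | Power, Pearson | Power, CMH | Power, CMH with continuity correction |
|---|---|---|---|---|---|
| 0 | 0.048 | 0.049 | 0.787 | 0.789 | 0.682 |
| 20 | 0.043 | 0.049 | 0.790 | 0.801 | 0.692 |
| 40 | 0.030 | 0.050 | 0.800 | 0.831 | 0.725 |

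The gain from uncorrected CMH is 0.3, 1.1 and 3.1 points (differences taken before rounding). The CMH type I error at a 40-point gap is 0.0503 before rounding. If cancer types split 20:10 or 10:20 per arm, the 40-point result is similar (0.799 against 0.834; 0.798 against 0.828). The Mantel-Haenszel risk difference interval with Sato variance has exact coverage of 0.941 to 0.954.

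**4. Events for the adjusted model.** Design effect: 30×0.38 + 30×0.09 = 14.1, or 14.1/7 = 2.0 per term. No effect: 60×0.38 = 22.8, or 22.8/7 = 3.3 per term. The chance of no events at all on intervention, where the treatment odds ratio is not estimable by maximum likelihood, is 0.91³⁰ = 5.9%. That holds whatever covariates are fitted.

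**5. Bias.** The documents give no covariate distributions, so six assumed scenarios were simulated (3,000 trials of 60 each). They ranged from covariates unrelated to cancer type to strongly related ones, with and without covariate effects.

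- *Maximum likelihood, failed fits excluded:* mean log odds ratio −2.17 to −2.42 against true values of −1.82 to −1.97, which is 19–24% too large.
- *Firth, all seven terms kept:* −1.83 to −1.99, an error of 0–2%.
- *Failures:* some coefficient failed in 6–15% of full fits, against about 6% for a model with arm and cancer type only.

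On the odds ratio scale, a true exp(−1.82) = 0.16 becomes about exp(−2.17) = 0.11.

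**The case against.** The planned test is valid, and the loss is small on any gap up to 20 points. The 3.1-point gain needs a 40-point gap that the documents do not support or exclude. Pearson's power rises slightly with the gap, so ignoring the strata never takes the trial below its gap-free power. The sentence about stratified randomisation can be read as concerning balance, not analysis, and cancer type is in the adjusted model. All of that stands, and it limits the size of the point.

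Fisher throughout is an extreme reading. The same Pearson-or-Fisher wording is used for baseline variables and may be shorthand for the usual expected-count rule, which costs only about 1 point. The smallest expected count at the design effect is about 14.1/2 = 7, so Pearson would usually be chosen. This is fair, but the rule is not written.

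Sixty analysed is the low end. If all 80 were analysed, Pearson would have 0.896 and Fisher 0.844, so Fisher's shortfall would disappear. The CMH gain would fall to 0.04, 0.4 and 1.8 points. Expected events would be 40×0.47 = 18.8 to 80×0.38 = 30.4 (2.7 to 4.3 per term), and the chance of no intervention-arm events 0.91⁴⁰ = 2.3%. This stands as a range, but 60 is the size on which the plan bases its power. The bias also persists at 80: simulations with covariates that have no effect gave maximum-likelihood estimates about 14–19% too large, with Firth within 2%.

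The inflation is less than half the standard deviation of the estimate (0.91 to 1.08) and affects a supporting model. That is true, but the bias is systematic, favours the intervention and is avoidable.

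**Conclusion.** The concern holds, as a recommended improvement and not a flaw that invalidates the trial. The unstratified test controls type I error but can fall well below 0.05: 0.043 at an assumed 20-point gap and 0.030 at 40. Uncorrected CMH restores the level, gains 0.3 to 3.1 power points at 60 analysed, and costs nothing when the cancer types have equal rates.

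The missing rule for the test costs about 1 point under the customary convention and about 10 if Fisher is used throughout. It also leaves the primary conclusion open in 9.7% of trials at the design effect.

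The event counts and the 5.9% chance of no intervention-arm events follow from the plan's own rates. The 19–24% overstatement of the log odds ratio rests on assumed covariate distributions, but it appears even when the covariates are independent and have no effect.

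**What to change.** In section 5.1:

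- **Primary test.** Name one: the Cochran-Mantel-Haenszel test stratified by cancer type, without continuity correction, two-sided 0.05. The correction must be excluded explicitly, because with it power falls below that of the planned Pearson test.
- **Primary estimate.** Report the Mantel-Haenszel risk difference with a 95% confidence interval (Sato variance), and the risk difference within each cancer type descriptively.
- **Sensitivity analysis.** Keep the unstratified Pearson test and delete the open Pearson-or-Fisher choice for the primary endpoint.
- **Adjusted model.** Keep all six covariates, state that the list is final, and fit the model with Firth's penalty and profile penalised-likelihood intervals.

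The cost is wording only. Cancer type is already recorded and used at randomisation. No patients, visits or data are added, and no prespecified covariate is dropped.

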Universal bacterial decolonization using similar strategies to what we are proposing have been shown to be safe and cost effective in other disease states, and is

now the standard of care in the intensive care unit and prior to orthopedic surgery in order to prevent infectious complications. For example, Huang et al found that universal SA decolonization with chlorhexidine and mupirocin dramatically decreased methicillin resistant staphylococcus aureus (MRSA) prevalence and MRSA-associated hospitalizations in a county-wide study.⁹ A recent systematic review of 19 studies showed that there was a reduction in surgical site infections and wound complications after institution of a SA screening and decolonization protocol.¹⁰

This study will focus on preventing RD in patients with breast and head/neck cancer, as these cancer types are associated with the highest incidence of RD. Anogenital cancers will not be included in this study, as too few patients from this category were recruited in our preliminary study to achieve statistical significance. Furthermore, this study excludes patients receiving RT for palliative intent as these patients receive few treatments and are unlikely to develop radiation dermatitis. By implementing a similar decolonization protocol in patients receiving RT, we hope to prevent the development of RD and improve quality of life.

3. Objectives and endpoints:

1. The primary goal is to determine if bacterial decolonization prior to RT prevents development of high grade RD (grade 2-5). The primary endpoint is the incidence of high grade RD at the end of the trial.
2. The secondary goal is to assess if the intervention improves quality of life compared to the control arm. The secondary endpoint is the quality of life, assessed by the Skindex-16.

4. Study Design:

4.1 Subject inclusion criteria:

1. Age ≥ 18
2. Diagnosis of a solid tumor of the breast or head and neck with plans for fractionated RT (≥ 15 fractions) with curative intent, including post-operative patients deemed eligible for RT by their surgeons and radiation oncologists

4.2 Patient exclusion criteria:

1. Prior RT to the region of interest
2. Existing dermatologic condition affecting the treatment area (eg: atopic dermatitis, psoriasis, and non-healing wounds)
3. Known allergy to chlorhexidine or mupirocin

4.3 Recruitment:

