Chlorhexidine and mupirocin will be prescribed by the principal investigator prior to the start of radiation therapy, at no cost to the patient. Patients will be supplied with a calendar showing the dates of decolonization and asked to document their decolonization regimen to monitor for compliance. Standardized photographs of the radiated area will be taken at baseline, and at the end of RT for purposes of grading. Should a patient refuse photographs, they may still participate in the study. Grading scores from the treating radiation oncologist's note in the electronic health record will be used in place of clinical photographs. Research funds from the division of dermatology and radiation oncology will be used to pay for bacterial culture swabs, wound culture laboratory fees, mupirocin, and chlorhexidine solutions. Should a patient in any treatment arm develop symptomatic RD or RD that is grade 2 or higher, the patient will be treated by the radiation oncologist. There is no restriction on use of topical or oral antibiotics as needed during the study. Patients may be treated by the radiation oncologist with other topical preparations including Aquaphor and/or silver sulfadiazine regardless of treatment arm.

The SKINDEX-16 questionnaire will be used prior to initiation of RT and at completion of RT to assess whether decolonization can improve patient quality of life. Validated in 2001, this questionnaire assesses domains of symptoms, emotions, and functioning. This questionnaire is commonly used in the evaluation of dermatologic diseases including RD, as it has demonstrated both content and construct validity in previous studies.¹¹ For example, one recent clinical trial that assessed mometasone furoate for the prevention of RD in breast cancer patients also utilized the SKINDEX-16 to assess quality of life as a secondary measure.¹² Furthermore, our preliminary study showed that patients with more severe RD were impacted more severely than patients without RD in all three domains (data submitted for publication).

Finally, de-identified samples from superficial skin swabs will be placed in a storage buffer meant to preserve bacterial nucleotides and kept in a freezer at -80C for

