future microbiome analysis. Bacterial RNA and DNA will then be extracted from the samples in order to perform skin microbiome analysis via whole-community metagenomics sequencing and RNA transcriptomics sequencing. Of note, only bacterial samples from culture swabs will be stored for future microbiome analysis of the skin flora. No DNA from participants will be stored.

Study evaluations will include:

Before RT and within two weeks of completion of RT:

- Bacterial cultures obtained via a superficial swab from (1) the nares, (2) skin at the irradiated site and (3) contralateral or other non-radiated skin. This is a non-invasive test using a cotton-tipped applicator inserted into the nostrils or rubbed on the skin.
- Superficial swabs from the same 3 sites will be obtained in the same manner to be stored in a -80° C freezer for future de-identified microbiome analyses.
- Standardized photographs of skin at radiated site to be graded by a dermatologist blinded to study arm. Additional photographs or notes from the chart may be taken in the case of that severe RD develops during treatment.
- Quality of Life assessment using the Skindex-16 questionnaire.¹⁰

Before and during RT:

- Patients will be asked to initial each date on the supplied calendar when they complete the decolonization protocol in order to assess compliance.

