Already in place in and distinct from the study, all safety monitor and reporting will be done by the standard of care and protocols of the Montefiore Center for Cancer Care and department of radiation oncology. There will be no Data Monitoring Committee. Any serious events will be reported to both the study PI and IRB.

The study PI, co-investigators and key personnel will be charged with assuring data accuracy and protocol compliance, interim monitoring of accumulated data from research activities to assure the continuing safety of participants, relevance of the study question, appropriateness of the study, and integrity of the accumulating data.

7. Appendix

Figure 1. Common Terminology Criteria for Adverse Events (CTCAE) Version 5.0 for Radiation Dermatitis

Injury, poisoning and procedural complications					
CTCE Term	Grade 1	Grade 2	Grade 3	Grade 4	Grade 5
Dermatitis radiation	Faint erythema or dry desquamation	Moderate to brisk erythema; patchy moist desquamation; mostly confined to skin folds and creases; moderate erythema	Moist desquamation in areas other than skin folds and creases; bleeding induced by minor trauma or abrasion	Life-threatening consequences; skin necrosis or ulceration of full thickness dermis; spontaneous bleeding from involved site; skin graft indicated	Death

*Dermatitis Radiation Definition: A finding of cutaneous inflammatory reaction occurring as a result of exposure to biologically effective doses of ionizing radiation

*Navigational Note: Synonym: Radiation induced skin toxicities (CTCAE v3.0)

Figure 2. Skindex-16

THESE QUESTIONS CONCERN THE SKIN CONDITION WHICH HAS BOthered YOU THE MOST DURING THE PAST WEEK

During the past week, how often have you been bothered by:

	Never Bothered ↓	·	Always Bothered ↓
1. Your skin condition itching			
2. Your skin condition burning or stinging			
3. Your skin condition hurting			
4. Your skin condition being irritated			
5. The persistence / reoccurrence of your skin condition			

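### The between-arm Skindex-16 regression does not name baseline Skindex-16 as a covariate; naming it is an efficiency improvement whose worst-case price is about 2% of variance at 60 patients

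*Combined protocol and SAP*

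**What the plan says.** Section 3 makes quality of life, measured by Skindex-16, the only secondary endpoint. Section 5.1 compares it between arms in two ways. The unadjusted comparison is a t-test on change: "The 2-sample t-test will be used to compare the QoL score change from baseline to the end of radiotherapy between the two arms". The adjusted comparison is a regression of the same change: "Linear regression models will be used to compare the changes in QoL scores between the 2 arms while adjusting for covariates including age". The covariate clause in full is "adjusting for covariates including age, gender, BMI, cancer type, radiation dose, and concurrent chemotherapy". Baseline Skindex-16 is not named there or anywhere else in the document.

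The baseline score is collected. Section 4.4 says "The SKINDEX-16 questionnaire will be used prior to initiation of RT and at completion of RT", its list of evaluations before and after radiotherapy repeats the item, and the calendar in section 4.5 schedules it at screening for all participants.

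Two places bear on how much baseline scores will vary. Section 4.2 excludes patients with an "Existing dermatologic condition affecting the treatment area". The questionnaire in the Appendix (Figure 2) names no body site and asks about "THE SKIN CONDITION WHICH HAS BOthered YOU THE MOST DURING THE PAST WEEK".

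**The concern.** A change score subtracts baseline with a coefficient of exactly 1. If the true slope of end score on baseline differs from 1, the subtraction removes too much or too little, and avoidable noise stays in the arm comparison. Adding baseline to the change regression estimates the slope, and gives the same arm effect as regressing the end score on arm and baseline.

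The stake is precision. Skindex-16 is to be analyzed in about 30 patients per arm, and no power is stated for it. At that size some chance imbalance is expected: the standard error of the baseline difference between arms is sqrt(2/30) = 0.26 baseline SDs. Over repeated randomizations the change-score estimate is unbiased. Given a particular observed imbalance d, it is shifted by (slope − 1) × d, and under a linear model baseline adjustment removes that shift. Finally, an open covariate list leaves the decision on baseline until data have been seen. Naming it now closes that choice.

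**Working it through.** **Inputs from the plan.** Recruitment of 80 with 25% attrition gives 80 × (1 − 0.25) = 60 analyzed, 30 per arm, as section 5.1 states. Six covariates are named, each taken here as a single term. The plan gives no Skindex-16 SD, pre/post correlation or power, so there is no plan figure for this endpoint to reproduce.

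**Assumed inputs.** Let k = baseline SD / end SD and ρ = pre/post correlation. The ranges shown are k = 0.25 to 1 and ρ = 0.2 to 0.6.

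**Step 1: large-sample effect.** In units of the end-score variance, change has variance 1 + k² − 2ρk, and the baseline-adjusted score has variance 1 − ρ². The difference is (k − ρ)², which is never negative. The ratio, without baseline over with baseline, is

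L = (1 + k² − 2ρk) / (1 − ρ²) = 1 + (k − ρ)² / (1 − ρ²).

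In large samples, adding baseline cannot increase the variance. It gains nothing when k = ρ, where the true slope ρ/k equals 1.

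**Step 2: price of one more covariate.** With p normal covariates independent of arm, the expected variance of the arm effect is inflated by (n − 3)/(n − 3 − p). For n = 60 this is 57/51 with six covariates and 57/50 with seven. Adding baseline therefore multiplies the variance by 51/50 = 1.020 when baseline explains nothing further. Residual degrees of freedom fall from 60 − 8 = 52 to 51. For other numbers analyzed the price is 71/70 (1.4%) at 80, 41/40 (2.5%) at 50 and 31/30 (3.3%) at 40.

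**Step 3: net ratio at 60 patients.** L × 50/51. Values above 1 favor naming baseline.

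| k | ρ = 0.2 | ρ = 0.4 | ρ = 0.6 |
|---|---|---|---|
| 0.25 | 0.98 | 1.01 | 1.17 |
| 0.50 | 1.07 | 0.99 | 1.00 |
| 0.75 | 1.29 | 1.12 | 1.01 |
| 1.00 | 1.63 | 1.40 | 1.23 |

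Example, k = 0.5 and ρ = 0.2: (1 + 0.25 − 0.2)/0.96 = 1.094, and 1.094 × 50/51 = 1.07. The minimum is 50/51 = 0.98, at k = ρ.

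**Step 4: when the ratio reaches 1.10.** This needs L ≥ 1.10 × 51/50 = 1.122, so |k − ρ| ≥ sqrt(0.122 × (1 − ρ²)). The result is k ≥ 0.54, 0.72 and 0.88 at ρ = 0.2, 0.4 and 0.6, or k ≤ 0.08 and k ≤ 0.32 at ρ = 0.4 and 0.6.

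**Step 5: simulation check.** With 30 per arm, bivariate normal scores, six covariates unrelated to the score and 60,000 trials, the ratio at k = ρ (0.2 to 0.6) was 0.979 to 0.981, and all 12 grid values lay within 0.02 of the formula. A separate simulation of 20,000 trials gave a price of 1.018 at k = ρ = 0.5. Both models had mean arm effects near zero under no true effect.

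**Step 6: baseline clustered at zero.** A 0–100 scale was assumed, with 40,000 trials. Non-zero baseline scores were exponential, with mean 15 in the first two cases and 25 in the third. End scores were 5% zero and otherwise gamma with shape 1.5 and mean 35. All scores were capped at 100. Columns are copula correlations; the observed correlations were 0.14 to 0.52.

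| Baseline | 0.2 | 0.4 | 0.6 |
|---|---|---|---|
| 70% at zero, k = 0.41 | 1.06 | 1.00 | 0.99 |
| 50% at zero, k = 0.50 | 1.10 | 1.02 | 0.99 |
| 50% at zero, k = 0.79 | 1.38 | 1.22 | 1.08 |

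**The case against.** The strongest reply is that nothing here is wrong. Change-score analysis is legitimate, the covariate list is open, and this is a secondary endpoint with no power claim. The benefit may also be close to nil in the setting the documents best support. Skin disease in the treatment area is excluded at entry, while section 2 puts radiation dermatitis at up to 95% of patients, so baseline scores should be less spread than end scores. At k = 0.5 the ratios are 1.07, 0.99 and 1.00, which moves the confidence interval width by about 3% or less (sqrt 1.07 = 1.034). Of the twelve values above with k at or below 0.5, normal and zero-clustered together, ten lie between 0.98 and 1.07.

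Most of this stands as a limit on the size of the gain. It does not make the change unsound. The exclusion covers the treatment area only, and the questionnaire is not tied to that site, so baseline spread is possible and the documents do not settle it. An open list permits baseline adjustment without committing to it.

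The 2% cap is also conditional. It is an expected value at 60 patients, and rises to 2.5% at 50 and 3.3% at 40. That stands too, but the price remains small, and 60 already allows for the planned attrition.

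**Conclusion.** The concern holds as an efficiency improvement on a secondary endpoint. The planned t-test and regression are valid and unbiased under randomization, and the primary endpoint is untouched. The payoff is lopsided: an expected loss of at most about 2% of variance at 60 analyzed patients, against a gain that may be negligible or substantial (a ratio of up to 1.63 in the range examined).

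The cap rests on six single-term covariates independent of arm. The gain rests on assumed SD ratios and correlations, and cannot be predicted from the documents. Baseline should be named because the cost is small and bounded and the data are already collected, not because a particular gain can be promised.

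**What to change.** In the secondary endpoint paragraph of section 5.1, add the baseline Skindex-16 score by name to the linear regression covariates, meaning the baseline value of the same score whose change is analyzed. State that the baseline-adjusted mean difference with its 95% CI is the between-arm quality-of-life estimate. Keep the planned change-score t-test alongside it.

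The change is to wording only and needs no new data. It costs one residual degree of freedom (52 to 51) and at most about 2% of variance at 30 per arm.
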